10.7.3 Multiple Comparisons

In order to control the overall Type I error rate for the analyses of the planned primary and secondary endpoints, a fixed-sequence method will be utilized. Under this methodology, all endpoints will be ordered sequentially; testing will begin with the first endpoint (primary endpoint) at the full alpha level and continue through the sequence only until an endpoint is not statistically significant. The sequence of testing will be as follows:

- 1. Time to alleviation of COVID-19-related symptoms of cough, dyspnea, chills, feeling feverish, repeated shaking with chills, muscle pain, headache, sore throat, and new loss of taste or smell, defined as symptom-free for a continuous period of ≥ 24 hours (ie, ≥ 3 AM/PM assessments) by day 30
- Percentage of patients with alleviation of COVID-19-related symptoms of cough, dyspnea, chills, feeling feverish, repeated shaking with chills, muscle pain, headache, sore throat, and new loss of taste or smell, defined as symptom-free for a continuous period of ≥ 24 hours (ie, ≥ 3 AM/PM assessments) by day 14
- Percentage of patients with alleviation of COVID-19-related symptoms of cough, dyspnea, chills, feeling feverish, repeated shaking with chills, muscle pain, headache, sore throat, and new loss of taste or smell, defined as symptom-free for a continuous period of ≥ 24 hours (ie, ≥ 3 AM/PM assessments) by day 7
- Percentage of patients with alleviation of COVID-19-related symptoms of cough, dyspnea, chills, feeling feverish, repeated shaking with chills, muscle pain, headache, sore throat, and new loss of taste or smell, defined as symptom-free for a continuous period of ≥ 24 hours (ie, ≥ 3 AM/PM assessments) by day 30
- 5. Change from baseline in oxygen saturation levels at day 7
- 6. Change from baseline in COVID-19 viral load in nasopharyngeal sample at day 30

- 7. Percentage of patients with subsequent emergency department visit or hospital admission for reasons attributable to COVID-19 by day 30
- 8. Time to hospital admission or death
- 9. Percentage of patients with hospital admission or death by day 30
- 10. All-cause mortality by day 30
- 11. COVID-19-related mortality by day 30

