The primary efficacy variable is time to alleviation of COVID-19-related symptoms of cough, dyspnea, chills, feeling feverish, repeated shaking with chills, muscle pain, headache, sore throat, and new loss of taste or smell, defined as symptom-free for a continuous period of \geq 24 hours (ie, \geq 3 AM/PM assessments) by day 30. The primary analysis will be based on the intent-to-treat population (all randomized patients). To increase precision of treatment effect estimation and inference, a Cox proportional hazards model will be used to allow for inclusion of additional prespecified prognostic baseline covariates. The median time to event and 95% confidence intervals will be summarized by treatment arm, and Kaplan-Meier estimates of the survival curves will also be generated. The secondary efficacy endpoints of percentage of patients with hospital admission or death by day 30; all-cause mortality by day 30; COVID-19-related mortality by day 30; percentage of patients with subsequent emergency department visit or hospital admission for reasons attributable to COVID-19 by day 30; and percentage of patients with alleviation of COVID-19-related symptoms of cough, dyspnea, chills, feeling feverish, repeated shaking with chills, muscle pain, headache, sore throat, and new loss of taste or smell, defined as symptom-free for a continuous period of ≥ 24 hours (ie, ≥ 3 AM/PM assessments) by day 7, by day 14, and by day 30 will be analyzed using a logistic regression model. This will improve the precision of treatment effect estimation and inference by allowing for baseline covariate adjustments to be included in the model. Analysis of the secondary efficacy endpoint of time to hospital admission or death will be performed using the same method as that used for the primary efficacy endpoint. The secondary efficacy endpoint of change from baseline in oxygen saturation levels will be summarized descriptively at all timepoints captured in the eDiary. The secondary efficacy endpoint of change from baseline in COVID-19 viral load in nasopharyngeal sample at day 30 will be summarized descriptively.

Safety

The safety population will include all randomized patients who receive at least 1 dose of double-blind study medication. Safety will be evaluated by summarizing the incidence of adverse events. Comparative analyses will be done on adverse events of special interest (eg, oral candidiasis).

Interim Safety Review

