4.2 Secondary Objectives

The secondary study objectives are:

- to assess whether treatment with ciclesonide MDI plus standard supportive care reduces the incidence of hospital admissions or death compared with placebo plus standard supportive care in non-hospitalized patients with symptomatic COVID-19 infection
- to assess whether treatment with ciclesonide MDI plus standard supportive care reduces all-cause mortality compared with placebo plus standard supportive care in non-hospitalized patients with symptomatic COVID-19 infection
- to assess whether treatment with ciclesonide MDI plus standard supportive care reduces COVID-19-related mortality compared with placebo plus standard supportive care in non-hospitalized patients with symptomatic COVID-19 infection
- to assess whether treatment with ciclesonide MDI plus standard supportive care reduces the incidence of subsequent emergency department visits or hospital admissions for reasons attributable to COVID-19 compared with placebo plus standard supportive care in non-hospitalized patients with symptomatic COVID-19 infection
- to assess whether treatment with ciclesonide MDI plus standard supportive care increases the percentage of patients with alleviation of COVID 19-related symptoms of cough, dyspnea, chills, feeling feverish, repeated shaking with chills, muscle pain, headache, sore throat, and new loss of taste or smell compared with placebo plus standard supportive care in non-hospitalized patients with symptomatic COVID-19 infection
- to assess whether treatment with ciclesonide MDI plus standard supportive care increases the time to hospital admission or death compared with placebo plus standard supportive care in non-hospitalized patients with symptomatic COVID-19 infection
- to assess the impact of treatment with ciclesonide MDI plus standard supportive care on oxygen saturation levels compared with placebo plus standard supportive care in non-hospitalized patients with symptomatic COVID-19 infection
- to assess the impact of treatment with ciclesonide MDI plus standard supportive care on COVID-19 viral load compared with placebo plus standard supportive care in non-hospitalized patients with symptomatic COVID-19 infection

• to assess the safety of ciclesonide MDI plus standard supportive care compared with placebo plus standard supportive care in non-hospitalized patients with symptomatic COVID-19 infection

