4.3.2 Key Secondary Endpoint Estimand

The attributes of the estimand for the key secondary endpoint included in the multiplicity control procedure of this trial are:

- 1. Treatment regimens: ciclesonide and placebo
- 2. Populations of interest: patients meeting inclusion/exclusion criteria grouped according to randomized treatment assignment reflect the target population
- 3. Patient-level outcome: binary indicator of alleviation of COVID-19-related symptoms of cough, dyspnea, chills, feeling feverish, repeated shaking with chills, muscle pain, headache, sore throat, and new loss of taste or smell, defined as symptom-free for a continuous period of \geq 24 hours (ie, \geq 3 AM/PM assessments) by day 14
- 4. Intercurrent events: regardless of the use of rescue medications, protocol violations, or investigational product discontinuation
- 5. Population-level summary measure: difference in response probabilities between treatment regimens

The **treatment-policy strategy** for this estimand is the difference in probabilities of alleviation of COVID-19-related symptoms of cough, dyspnea, chills, feeling feverish, repeated shaking with chills, muscle pain, headache, sore throat, and new loss of taste or smell, defined as symptom-free for a continuous period of ≥ 24 hours (ie, ≥ 3 AM/PM assessments) by day 14 between those assigned to ciclesonide and those assigned to placebo, regardless of patient's use of rescue medications, protocol violations, or investigational product discontinuation. Therefore, for all patients in the ITT analysis set, all observed on-study data will be analyzed in accordance with the definition set forth above for intercurrent events.

Since death and hospitalization are not part of this key secondary endpoint patient level-outcome definition, a composite strategy will be used to handle these situations. If a patient dies or is hospitalized, then the value attributed in that scenario would be failure to achieve alleviation of COVID-19-related symptoms which ascribes the most unfavorable value.

Estimands for other secondary efficacy endpoints included in the multiplicity control procedure (section 10.7.3) will be described in the Statistical Analysis Plan (SAP).

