10.7.2 Secondary Efficacy Endpoints

The secondary efficacy endpoints of percentage of patients with hospital admission or death by day 30; all-cause mortality by day 30; COVID-19-related mortality by day 30; percentage of patients with subsequent emergency department visit or hospital admission for reasons attributable to COVID-19 by day 30; and percentage of patients with alleviation of COVID-19-related symptoms of cough, dyspnea, chills, feeling feverish, repeated shaking with chills, muscle pain, headache, sore throat, and new loss of taste or smell, defined as symptom-free for a continuous period of \geq 24 hours (ie, \geq 3 AM/PM assessments) by day 7, by day 14, and by day 30 will be analyzed using a logistic regression model. To improve the precisions on treatment effect estimation and inference, baseline covariate adjustments will be made for gender, age, race, and body mass index, as these are known COVID-19 risk factors. Analysis of the secondary efficacy endpoint of time to hospital admission or death will be performed using the same method as that used for the primary efficacy endpoint. The secondary efficacy endpoint of change from baseline in oxygen saturation levels will be summarized descriptively at all time points captured in the eDiary. The secondary efficacy endpoint of change from baseline in COVID-19 viral load in nasopharyngeal sample at day 30 will be summarized descriptively.

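### Steps 5 and 6 of the fixed testing sequence are significance gates, but the protocol plans only descriptive summaries for them, so steps 7 to 11 cannot be formally reached as written

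*Combined protocol and SAP*

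**What the plan says.** Section 10.7.3 sets up a fixed sequence to control the overall Type I error. Testing starts with the primary endpoint at full alpha and is to "continue through the sequence only until an endpoint is not statistically significant". Step 5 is "Change from baseline in oxygen saturation levels at day 7"; step 6 is the change in nasopharyngeal viral load at day 30.

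Section 10.7.2 gives the analysis of these two endpoints. For the first, "change from baseline in oxygen saturation levels will be summarized descriptively at all time points captured in the eDiary". For the second, "change from baseline in COVID-19 viral load in nasopharyngeal sample at day 30 will be summarized descriptively". The Statistical Methods part of the synopsis agrees: "change from baseline in oxygen saturation levels will be summarized descriptively at all timepoints captured in the eDiary", with a matching statement for viral load.

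The other secondary endpoints have inferential methods in section 10.7.2. The binary ones use covariate-adjusted logistic regression. Analysis of "time to hospital admission or death will be performed using the same method as that used for the primary efficacy endpoint", which section 10.7.1 gives as a Cox model.

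The objectives in section 4.2 do ask for a comparison: "to assess the impact of treatment with ciclesonide MDI plus standard supportive care on oxygen saturation levels compared with placebo", and likewise for viral load. Section 4.3.2 adds: "Estimands for other secondary efficacy endpoints included in the multiplicity control procedure (section 10.7.3) will be described in the Statistical Analysis Plan". The opening of section 10 says that a SAP will explain the methods in more detail, will be final before unblinding, and may change the protocol's methods without an amendment. No SAP text is in the supplied file.

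**The concern.** A fixed sequence needs a significance verdict at every step before the next one may be tested. A descriptive summary gives no such verdict. Two consecutive steps in the middle of the chain are therefore gates with no stated way to decide whether they open.

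At stake are formal claims on steps 5 to 11. Steps 7 to 11 are the harder outcomes: emergency visit or admission for COVID-19, time to admission or death, admission or death by day 30, all-cause mortality and COVID-19 mortality. Each has a named model, but none can be reached through the sequence as described.

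**Working it through.** **1. Each step against its stated method**

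| Step (10.7.3) | Endpoint | Method (10.7.1, 10.7.2) |
|---|---|---|
| 1 | Time to alleviation | Cox |
| 2, 3, 4 | Alleviation by day 14, 7, 30 | Logistic |
| 5 | Saturation change, day 7 | Descriptive only |
| 6 | Viral load change, day 30 | Descriptive only |
| 7 | Emergency visit or admission for COVID-19 | Logistic |
| 8 | Time to admission or death | Cox |
| 9, 10, 11 | Admission or death; all-cause mortality; COVID-19 mortality | Logistic |

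Nine of 11 steps have an inferential method and two have none. Section 10.3.1 does not fill the gap: for continuous variables it lists n, mean, standard deviation, median and range, and no test. No skip rule is given. The last step that can be completed from the stated methods is step 4, and five steps (7 to 11) lie beyond the gap.

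There is a second, smaller gap at step 5. It fixes day 7, but readings are taken twice daily and 10.7.2 speaks of all diary time points. Which day-7 reading counts is not stated.

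**2. The plan's own figure**

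Inputs from section 10.1: hazard ratio about 1.58, power 90%, alpha 0.05, 1:1 allocation. Sidedness is not stated; two-sided reproduces the figure. Schoenfeld's formula gives

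events = 4 × (1.960 + 1.282)² / (ln 1.58)² = 42.03 / 0.2092 = 200.9, rounded up to 201.

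This matches the plan. The finding does not depend on it, but it supports using the same medians below.

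**3. Illustration: how likely is the trial to meet the gap?**

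Assume exponential times with medians of 7 and 11 days (section 10.1), censoring at day 30 and no drop-out. The probability of alleviation by day t is 1 − 2^(−t/median):

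- day 7: 0.500 vs 0.357
- day 14: 0.750 vs 0.586
- day 30: 0.949 vs 0.849

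In 40,000 simulated trials per scenario (Monte Carlo standard error at most 0.0025), step 1 used a log-rank test and steps 2 to 4 used two-proportion z tests. Each was two-sided at 0.05 and counted only when it favoured ciclesonide. These unadjusted tests stand in for the planned Cox and logistic models.

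| Per arm | Pass 1 | Pass 1–2 | Pass 1–3 | Pass 1–4 |
|---|---|---|---|---|
| 200 (planned) | 0.990 | 0.936 | 0.801 | 0.758 |
| 116 (the plan's 90%-power size) | 0.901 | 0.744 | 0.539 | 0.449 |

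At 116 per arm the simulated step-1 power of 0.901 and mean of 208.6 events agree reasonably with the plan's 90% and about 201.

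A cross-check at 200 per arm: the separate powers are 0.990 (step 1), 0.939 (day 14), 0.828 (day 7) and 0.914 (day 30). Independence would give 0.990 × 0.939 × 0.828 × 0.914 = 0.70, and the joint probability cannot exceed the smallest, 0.828. The simulated 0.758 lies between, as expected for tests that share the same event times.

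These probabilities say how often the gap would be met. They do not measure the defect, since they are the same whether or not steps 5 and 6 have a test. The documents give no effect sizes for steps 5 and 6 and no event rates for steps 7 to 11, so the number of later claims lost cannot be computed.

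**The case against.** The strongest reply is that the SAP will settle this. Section 10 presents the SAP as the fuller account of the methods, and section 4.3.2 promises the estimands for the sequenced endpoints there. A summary and a test can also coexist: listing the endpoints in a testing sequence, together with the objectives in section 4.2, shows that a comparison is intended.

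Much of this stands. It limits the finding to the protocol text, because an unseen SAP may already name the tests. It does not remove the conflict. An estimand fixes the outcome and the summary measure but not the test, and a SAP that merely elaborated the stated method would still be descriptive. Someone has to make a deliberate change.

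A reader might infer that the trial has no confirmatory route to its hospital admission and mortality endpoints. The documents do not support that, since the SAP is not in the file and section 10 lets it supply the tests. A reader might also infer that Type I error is inflated. It is not: a chain that stops at step 4 is conservative. Error control would be at risk only if a test were chosen, or the gates skipped, after unblinding, and section 10 requires the SAP to be final before then.

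**Conclusion.** The concern holds for the protocol as supplied, and it should be fixed. Sections 10.7.2 and 10.7.3 conflict for two of 11 steps, and five further steps sit behind those two. Followed literally, the sequence ends at step 4, and formal claims on steps 5 to 11 are lost. The primary endpoint and steps 2 to 4, including the key secondary endpoint, are untouched.

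This rests on the text alone and needs no numerical assumption. The chance of arriving at the gap, about 0.76 at 200 per arm and about 0.45 at 116 per arm, is illustrative. It depends on the plan's medians, exponential times, no drop-out and unadjusted tests.

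**What to change.** Before unblinding, state in the SAP one prespecified test for each of steps 5 and 6. An example is ANCOVA on the change, adjusted for the baseline value and the planned covariates (gender, age, race, body mass index). Fix which day-7 saturation reading is used (AM or PM) and how missing values and undetectable viral loads are handled. Record that this replaces the descriptive-only statement in section 10.7.2.

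If the sponsor prefers to keep both endpoints descriptive, remove them from the sequence so that step 7 follows step 4.

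Either change is wording only, and section 10 allows it in the SAP without a protocol amendment. Naming tests keeps steps 7 to 11 behind two gates whose power the documents do not give. Removing the two endpoints gives up formal claims on saturation and viral load. If the existing SAP already names the tests, it is enough to confirm that it does so and that it overrides section 10.7.2.

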10.8 Analysis of Safety Data

The incidence of adverse events will be summarized by Medical Dictionary for Regulatory Activities (MedDRA) body system classification and preferred term. All treatment-emergent adverse events will be summarized overall and for each body system and preferred term by treatment group, relationship to investigational product, and severity. For tabulations by severity, only a patient's most severe event within the category (eg, overall, body system, or preferred term) will be counted. "Treatment-emergent" will be defined as starting or worsening after the first dose of investigational product. If the start date is missing, the event is assumed to be treatment-emergent. All serious adverse events will be tabulated.

In order to understand specific adverse events of special interest (eg, oral candidiasis), analyses will be conducted to compare the treatment arms with respect to differences in cumulative incidence rates with accompanying confidence intervals. Details will be provided in the SAP.

10.9 Interim Safety Review

The DMC will conduct a review of blinded safety data once 100 subjects have been enrolled. Details of the interim safety review will be described in detail in the DMC charter.

11 QUALITY CONTROL AND QUALITY ASSURANCE

11.1 Conduct of the Study

Covis shall implement and maintain quality control and quality assurance procedures with written Standard Operating Procedures to ensure that the study is conducted and data are generated, documented, and reported in compliance with the protocol, ICH Good Clinical Practice (GCP), and applicable regulatory requirements.

This study is to be conducted according to globally accepted standards of GCP (as defined in the ICH E6 Guideline for GCP, 1 May 1996), in agreement with the latest revision of the Declaration of Helsinki and in keeping with local regulations.

The investigator should ensure that all persons assisting with the trial are adequately qualified, informed about the protocol, any amendments to the protocol, the study treatments, and their trial-related duties and functions.

The investigator should maintain a list of sub-investigators and other appropriately qualified persons to whom he or she has delegated significant trial-related duties.

The investigator may not deviate from the protocol without a formal protocol amendment having been established and approved by an appropriate Independent Ethics Committee (IEC)/IRB, except when necessary to eliminate immediate hazards to the patient or when the change(s) involve(s) only logistical or administrative aspects of the study. Any deviations may result in the patient having to be withdrawn from the study and render that patient nonevaluable.

11.2 Study Monitoring

Monitoring and auditing procedures, developed or endorsed by the sponsor, will be followed to comply with GCP guidelines. Access to the study documentation and medical records will be ensured.

The study will be monitored by the sponsor or its designee. Throughout the course of the study, the study monitor will make frequent contact with the investigator. This will include telephone/web calls, e-mails, and video conferences, if appropriate. During the remote interim monitoring visits, the status of the site will be discussed including, but not limited to the following: enrollment status, review of study data, and ICF process for newly enrolled patients.

As part of the data monitoring, source documents must be made available to the study monitor for remote review. Remote source data verification will be performed as specified in the clinical monitoring plan. The study monitor will also perform remote investigational product drug accountability and will perform reviews of the electronic investigator study file to ensure completeness of documentation in all respects of clinical study conduct and safety oversight.

Upon completion of the study, the study monitor will conduct a final review of the study files, after which the files should be secured for the appropriate time period. The investigator, or appointed delegate, will make themselves available over the phone or web, if needed, and will

cooperate in making documents available for inspection and responding to inquiries. In addition, the investigator will permit inspection of the study files by authorized representatives of the sponsor or regulatory agencies.

12 ETHICS

12.1 Independent Ethics Committee/Institutional Review Board

Prior to initiation of the study, the investigator will submit the study protocol, sample ICF, and any other documents that pertain to patient information, recruitment methods, and advertisements, to the IRB/IEC. The investigator must also submit any other information that may be requested to the IRB/IEC for review and approval. The investigator will request that the IRB/IEC provide written approval of the study and will keep on file records of approval of all documents pertaining to this study. A letter confirming the approval must be forwarded to the study monitor prior to initiation of this study. This letter will be forwarded to the sponsor prior to the initiation of the study.

The investigator must submit and, where necessary, obtain approval from the IRB/IEC for all subsequent protocol amendments and changes to the ICF. The investigator should notify the IRB/IEC of deviations from the protocol or serious adverse events occurring at the site, as well as other adverse event reports received by the sponsor, in accordance with local procedures.

The investigator will be responsible for obtaining annual IRB/IEC approval or renewal throughout the duration of the study.

